1.0 Study Summary

Title: Evaluating the Impact of the Bridge Clinic in Patients with Opioid Use Disorder

Study Aims:

- Aim 1: To determine whether referral to the Bridge Clinic reduces overall index hospital length of stay when compared to direct referral to a long-term outpatient addiction provider for patients with active opioid use disorder (OUD) being considered for medications-for-addiction treatment (MAT).
- Aim 2: To evaluate the effects of the same intervention in the same population on secondary outcomes including costs, care-linkage, readmission rates, self-reported buprenorphine or naltrexone fills, rate of known recurrent opioid use, and measures of overall quality of life.
- Aim 3: Evaluate fidelity outcomes including Bridge Clinic acceptance and attendance rates among those referred to Bridge Clinic and reasons why patients were not considered to be eligible for inclusion.
- Aim 4: Among the subgroup of patients with an infection for which a course of IV antibiotics is required, additionally evaluate whether access to the Bridge Clinic facilitates outpatient management of the antibiotic therapy, with consequent improvement in clinical (infection and mortality) and resource (inpatient days, time to discharge following a negative blood culture) outcomes.

Study Hypotheses:

- Primary: Among patients with active OUD being considered for MAT, index hospital length of stay will be shorter among patients randomized to referral to the Bridge Clinic than among patients randomized to no referral to the Bridge Clinic.
- Secondary: Among patients with active OUD being considered for MAT, total costs, readmission rates, and rate of recurrent opioid use will be lower while successful care-linkage, self-reported buprenorphine or naltrexone prescription fill rates and quality of life will be higher among patients randomized to referral to the Bridge Clinic than among patients randomized to no referral to the Bridge Clinic.
- Exploratory: Among patients with active OUD being considered for MAT who also have an infection requiring IV antibiotics, referral to the Bridge Clinic will result in lower resource use without worse clinical outcomes when compared with not being referred to the Bridge clinic.

Study Population: Inpatients with OUD being considered for medications-for-addiction treatment (MAT) who have not previously utilized Bridge Clinic.

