6.0 Study Procedures

An enrolled patient will receive a referral to social work for “outpatient MAT”. The ACT social worker will approach the patients with resources for outpatient MAT determined by randomization (though the social worker can escalate patients in either condition to a higher level of care as appropriate after randomization). All patients will be offered usual information about outpatient MAT. Patients randomized to be eligible for referral to the Bridge Clinic will additionally receive information about the Bridge Clinic and this will be offered as an option during discussion of the plan for MAT. Patients who are randomized to not being offered a Bridge Clinic referral will not receive information about the Bridge Clinic and the Bridge Clinic will not be offered as an option.

Subsequent to comparator group assignment, patients will be followed to measure outcomes. All data will be captured from the medical record, financial systems, state-mandated reporting systems, and from other standard of care documentation. The data elements to be collected include the following:

Baseline demographics collected at time of enrollment

- Age
- Gender
- Race
- Ethnicity
- SES indicators

Primary Endpoint

- Overall index hospital length of stay

Principal Investigator: [name]

Version Date: April 7, 2022

Study Protocol: Evaluating the Impact of the Bridge Clinic in Patients with Opioid Use Disorder

Additional Endpoints collected for 16 weeks following randomization

- Costs of care (total costs, and costs for each admission and care resource used (e.g. Bridge Clinic))
- Linkage to MAT provider (attending at least one visit with a MAT provider)
- Self-reported buprenorphine-naloxone (or naltrexone) prescriptions filled
- Readmission
- ED visits
- Hospital and ED free days
- Recurrent opiate use
- Overall quality of life as measured by the Schwartz Outcome Scale-10 (SOS10)
- Overdose
- Death
- Cross-over to Bridge Clinic to community care or vice-versa

Additional Endpoints for patients with infection suitable for outpatient management, collected for 16 weeks following randomization

- New, persistent, or recurrent infection (as defined by a positive culture and/or change in antibiotic regimen)
- Completion of antibiotic therapy
- Days from negative blood culture to first hospital discharge

Implementation Measurements

- Acceptance of Bridge Clinic as a bridging provider
- Reasons for ineligibility

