### *Implementation Endpoints*

- a) Acceptance of Bridge Clinic as a bridging provider, defined by being physically checked in for at least 1 visit with the Bridge Clinic within 16 weeks of follow up.
- b) Reasons for ineligibility among participants screened, specifically:
  - o Absence of a qualifying OUD
  - o Previously linked with a MOUD provider either prior to or during the current visit?
  - o ACT determines the participant does not qualify

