### *Main Analysis*

The primary outcome variable (hospital index length of stay) will be compared between groups using an adjusted generalized linear model. Since the data are positive and may be skewed, like a gamma distribution, we may use a negative inverse link function, a proportional odds model, or transform the data.

In this analysis, group assignment is the main predictor variable. For drawing conclusions about the effect of the Bridge clinic, a critical p-value of 0.05 for the effect of treatment group assignment on the primary outcome will be used. The model will be adjusted for age, race, ethnicity, and area deprivation index. The influence of continuous variables will be assessed using restricted cubic splines with a minimum of three knots. We do not expect missingness in our primary outcome. If there are missing covariates, cases will not be excluded; we will use multiple imputation with predictive mean matching for missingness in adjusting covariates.

Secondary and implementation outcomes will be compared between study groups using adjusted generalized linear models, just as for the primary endpoint. Binary endpoints will use a logit link function. For counts, such as number of medication refills, either a zero-inflated Poisson or a negative binomial model will be fit.

Exploratory outcomes for OPAT patients will not be compared between study groups but will be reported by study group.

There may be missingness in secondary or implementation outcomes. If there are missing outcomes, these may be imputed if they occur in less than 5% of cases. Otherwise, the cohort for which the outcome is available will be described, along with the results of the model evaluating treatment effects in this cohort. All model results will be summarized with point estimates and 95% confidence intervals (CIs), which will be emphasized over p-values when reporting the results for secondary and implementation outcomes. No adjustments for multiplicity will be made.

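### The SAP orders a between-arm regression for its two implementation endpoints, but one has no arms and the other is open by design to only one arm

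*SAP*

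**What the plan says.** **Analysis instruction.** SAP, Main Analysis: "Secondary and implementation outcomes will be compared between study groups using adjusted generalized linear models", in the same manner as the primary endpoint, that is, with group assignment as the main predictor and covariate adjustment. It adds: "Binary endpoints will use a logit link function". The same section exempts the outcomes of patients on outpatient antibiotic therapy from comparison. It gives implementation outcomes no such exemption.

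**Endpoints it applies to.** SAP, Implementation Endpoints, lists two:
- (a) acceptance of the Bridge Clinic, defined as "being physically checked in for at least 1 visit with the Bridge Clinic within 16 weeks of follow up", which is a yes/no outcome for each patient;
- (b) a category recorded at screening, listed as "Reasons for ineligibility among participants screened".

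**Access in the control arm.** Protocol 6.0: patients randomized to no referral receive no information about the clinic, and "the Bridge Clinic will not be offered as an option".

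**What the Protocol wants.** Aim 3 asks for "Bridge Clinic acceptance and attendance rates among those referred to Bridge Clinic". Protocol 10.0 plans to characterize implementation measures and names no between-arm test for them.

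**Elsewhere in the SAP.** The overview under Statistical Approach mentions only secondary endpoints for comparison after the main analysis. Descriptive Analysis promises summaries of every outcome variable, overall and by arm, without statistical comparison. The Fidelity Endpoint defines cross-over by what the patient is offered at inpatient discharge.

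**The concern.** A between-arm model needs an outcome that patients in both arms can have, and patients who belong to an arm. Endpoint (b) fails the second condition and endpoint (a), by design, fails the first. An analyst who follows the sentence literally will meet one model with no group variable. The other either does not converge or returns a very large odds ratio that restates the allocation.

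What is at stake is limited. Aim 3 asks how many referred patients take up the clinic, and the ordered model does not estimate that. Following the sentence produces an uninterpretable estimate; dropping it at reporting becomes an unexplained deviation from the SAP.

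**Working it through.** The plan states no figure for this point, so there is none to reproduce. The check compares the endpoint definitions with the ordered model, then fits that model to counts built from the plan's own inputs.

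**Endpoint (b), ineligibility reasons.** Protocol 5.0 randomizes a patient only after eligibility is confirmed and collects the reason for non-enrolment from patients who are not enrolled. The SAP's Analysis dataset section takes in eligible participants. Randomized patients contributing an ineligibility reason: 0. The group term does not exist. The outcome is also a set of unordered categories, for which Main Analysis names no model.

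**Endpoint (a), acceptance.** Inputs:
- 168 patients per group (SAP, Sample Size Considerations; ratio 1:1);
- about 2/3 of referred patients make a first appointment (same section), so 168 × 2/3 = 112 check-ins and 56 without. This assumes that everyone randomized to the Bridge arm is referred;
- control check-ins *c*: 0 under the design. The documents give no rate, so values from 1 to 17 are assumptions.

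Unadjusted odds ratio: OR = (112/56) ÷ [*c*/(168 − *c*)] = 2 × (168 − *c*)/*c*.

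| Control check-ins *c* | OR | 95% CI (Wald) |
|---|---|---|
| 0 | infinite | 0 to infinity |
| 1 | 2 × 167/1 = 334 | 46 to 2448 |
| 2 | 2 × 166/2 = 166 | 40 to 694 |
| 5 | 2 × 163/5 = 65 | 25 to 168 |
| 8 | 2 × 160/8 = 40 | 18 to 87 |
| 17 | 2 × 151/17 = 18 | 10 to 32 |

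At *c* = 0 the logistic fit does not settle: the log odds ratio was 27.3 (SE about 27,000) after 25 iterations and 37.3 (SE about 4 million) after 100. This is quasi-complete separation, because the Bridge arm contains both outcomes and the control arm only one. Covariate adjustment does not help, since no covariate pattern in the control arm has an event.

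For *c* of 1 or more the model can be fitted, but the estimate is governed by *c*. Going from 1 to 5 control check-ins moves the odds ratio from 334 to 65 while Bridge arm uptake stays at 112/168.

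**The quantity Aim 3 needs.** 112/168 = 66.7%. The exact (Clopper–Pearson) 95% CI is 59.0% to 73.7%. The normal approximation agrees: 1.96 × √(0.667 × 0.333/168) = 0.071. If uptake differs from 2/3, the half-width with 168 patients is at most 1.96 × √(0.25/168) = 0.076.

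**The case against.** The strongest reply is that little is lost. Descriptive Analysis already covers all outcome variables by arm with frequencies and proportions, so the Bridge arm check-in rate will appear whatever the model does. That stands, and it is the main reason the point is minor. It does not cancel the instruction in Main Analysis, it promises no confidence interval, and it cannot be applied by arm to ineligibility reasons.

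A second reply is that control check-ins can occur. The Fidelity Endpoint anticipates that some usual-care patients will be offered the clinic, and acceptance is counted over 16 weeks. So the model is not strictly impossible, and the contrast in attendance does show how well the arms were separated. This also stands, but two counts and two proportions show that separation better than an adjusted odds ratio.

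A reader might infer stronger points that the documents do not support:
- *That the SAP defeats Aim 3.* The model is superfluous, but it does not displace the descriptive proportion.
- *That the trial will claim a significant effect on acceptance.* The 0.05 criterion is tied to the primary outcome. For implementation outcomes the SAP puts confidence intervals ahead of p-values.
- *That the comparison carries no information at all.* With cross-over it carries some, about adherence and contamination.
- *That a misleading result could arise for ineligibility reasons.* Patients without an arm cannot enter the model, so the likely outcome is a plain table.

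**Conclusion.** The instruction is wrong as written for both implementation endpoints. For ineligibility reasons it cannot be carried out. For acceptance it gives an infinite odds ratio if the control arm has no check-ins, and otherwise a large one (334 to 65 with 1 to 5 control check-ins) that measures only adherence and contamination. It also departs from the population named in Aim 3 and from the descriptive treatment in Protocol 10.0.

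Severity is minor. The primary endpoint, the secondary endpoints, the sample size, the significance level and data collection are all unaffected.

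The structural conclusion rests only on the endpoint definitions and the order of eligibility and randomization. The figures rest on 168 per arm, on 2/3 uptake applied to the whole Bridge arm, and on assumed control check-ins. Protocol 5.0 randomizes patients to being offered a referral, so those actually referred may be fewer than those randomized, and the two uptake rates may then differ.

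**What to change.** In SAP Main Analysis:

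1. Limit the between-group model sentence to secondary outcomes.
2. Align the two later statements that still attach modelling to implementation outcomes: the missing-outcome rule and the sentence on point estimates and confidence intervals.
3. Add text to this effect:

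> Acceptance will be reported as the proportion of patients randomized to the Bridge arm with at least one check-in within 16 weeks, with an exact 95% CI, and also among those in that arm who were actually referred. Check-ins by control patients will be reported as a separate count and proportion, as a measure of contamination. Reasons for ineligibility will be tabulated among screened patients who were not randomized, with no comparison between arms.

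The control check-in count should not be relabelled as cross-over. The Fidelity Endpoint defines cross-over by the offer at discharge, so a control patient may be offered the clinic and never attend, or attend later without that offer. The second acceptance denominator matches Aim 3.

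Cost: a few sentences in the SAP, no change to the sample size, and less modelling than now planned. The only additional item to confirm is that actual referral is recorded, so that the second denominator can be formed.

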Data will be abstracted from the EMR, REDCap and the Research Derivative (RD). The Research Derivative is a database of clinical and related data derived from the Medical Center's clinical systems and restructured for research. Data is repurposed from VU's enterprise data warehouse, which includes data from StarPanel, VPIMS, and ORMIS (Operating Room Management Information System), EPIC, Medipac, and HEO among others. The medical record number and other person identifiers are preserved within the database. Data types include reimbursement codes, clinical notes and documentation, nursing records, medication data, laboratory data, encounter and visit data, among others. Output may include structured data points, such as ICD 9 codes or encounter dates, semi-structured data such as laboratory tests and results, or unstructured data such as physician progress reports. The database is maintained by the Office of Research Informatics under the direction of [name].

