### *Secondary Endpoints*

Multiple secondary endpoints are prespecified for this trial. Secondary endpoints are collected for 16 weeks following randomization:

- a) Overall quality of life as measured by the Schwartz Outcome Scale-10 (SOS10). The SOS10 has ten questions scored on a 0 (never) to 6 (all or nearly all of the time) scale. A total score is computed as the sum across the 10 questions. If two questions are missing, a mean score can be imputed for the missing values to generate a total score. No further imputation will be used for this score. This is self-reported and captured at the 16-week follow-up call.
- b) Linkage to MOUD provider, defined as attending at least one visit with a MOUD provider after discharge, assessed by self-report at 16-week follow-up call.
- c) Self-reported buprenorphine-naloxone (or naltrexone) prescriptions filled (number filled) at the 16-week follow-up call.
- d) Any recurrent opioid use reported at the 16-week phone call follow-up.
- e) Number of recurrent opioid uses reported at the 16-week phone call follow-up.
- f) Number of ED visits or readmissions to VUH 16 weeks post discharge identified in the electronic medical record.
- g) Hospital and emergency department free days
  - a. Hospital free days will be calculated as a count of whole days during the 16 weeks the subject is not in the hospital. If the subject dies before the end of 16 weeks, hospital free days will be equal to -1.
  - b. Hospital and emergency department free days will be calculated as a count of whole days during the 16 weeks the subject is not in the emergency department or in the hospital. If the subject dies before the end of 16 weeks, emergency free days will be equal to -1.
- h) Any overdose reported at the 16-week phone call follow-up.
- i) Death in hospital or documented at the 16 week follow up or in the medical record.
- j) Costs of care, defined as total costs for all care episodes at VUMC 16 weeks post discharge.

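### Adjusting VUH utilization and VUMC cost for the same measure before admission would probably sharpen these secondary comparisons at little cost; the planned comparison is valid without it

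*SAP*

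**What the plan says.** Under Main Analysis, the SAP lists the covariates of the primary model: "The model will be adjusted for age, race, ethnicity, and area deprivation index". It then carries the approach over: "Secondary and implementation outcomes will be compared between study groups using adjusted generalized linear models, just as for the primary endpoint". For count outcomes it adds: "For counts, such as number of medication refills, either a zero-inflated Poisson or a negative binomial model will be fit". Continuous covariates are to be assessed with restricted cubic splines of at least three knots. For secondary outcomes, confidence intervals are to be given more weight than p-values.

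Two secondary endpoints are limited to one health system. Item f is "Number of ED visits or readmissions to VUH 16 weeks post discharge identified in the electronic medical record". Item j is "Costs of care, defined as total costs for all care episodes at VUMC 16 weeks post discharge".

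Neither document names prior visits, admissions or costs as a covariate. They are not among the baseline variables in Protocol section 6.0 or in the SAP's Descriptive Analysis, although the SAP list is expressly a minimum. Protocol section 10.0 promises adjustment for important covariates without naming any. No stratified randomization is described.

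On sources, Protocol section 6.0 describes the Research Derivative, which keeps medical record numbers: "Data types include reimbursement codes, clinical notes and documentation, nursing records, medication data, laboratory data, encounter and visit data, among others". The same section names financial systems as a separate source.

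**The concern.** Items f and j record only what happens at VUH or VUMC. Whether a patient habitually comes to this hospital plausibly drives both. Age, race, ethnicity and an area-level deprivation score do not measure that habit directly; the same measure in a period before the index admission does. Such a value is fixed before randomization and recorded in the same way in both arms.

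Lower readmission and lower total cost are among the secondary hypotheses in Protocol section 1.0. Since intervals will carry the message, their width matters. Leaving out a strong baseline predictor makes them wider than they need be, and a chance excess of frequent VUH users in one arm stays in the point estimate.

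**Working it through.** **Inputs from the documents.** 168 patients per group, 336 in total (Protocol section 10.0, Interim Analysis; SAP, Sample Size Considerations), allocated 1:1. The plan gives no power, standard deviation or pre/post correlation for items f and j, so it has no figure of its own to reproduce here. The 168 was derived for length of stay and serves below only as a headcount.

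**Assumed input.** ρ, the correlation between the prior measure and the outcome on the analysis scale, shown from 0 to 0.5.

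**Step 1: precision.** With a linear baseline covariate, residual variance is multiplied by 1 − ρ², interval width by √(1 − ρ²), and the equivalent number of patients is 336/(1 − ρ²).

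| ρ | Variance factor | Width factor | Equivalent patients |
|---|---|---|---|
| 0 | 1.00 | 1.00 | 336 |
| 0.2 | 0.96 | 0.980 | 350 |
| 0.3 | 0.91 | 0.954 | 369 |
| 0.5 | 0.75 | 0.866 | 448 |

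Intervals are therefore about 2%, 5% and 13% narrower at ρ = 0.2, 0.3 and 0.5.

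**Step 2: chance imbalance.** For a baseline measure in standard deviation units, the difference between arm means has standard deviation √(2/168) = 0.109, so its 95% range is ±1.96 × 0.109 = ±0.21. Without adjustment, this moves the outcome contrast by ρ times as much: up to about ±0.04, ±0.06 or ±0.11 outcome standard deviations at ρ = 0.2, 0.3 or 0.5.

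**Step 3: does this carry over to a count model?** The formula in Step 1 is for a linear model, so a negative binomial simulation was run with and without log(1 + prior count). Its assumptions are not from the documents: mean of 1 event per 16 weeks, log-normal frailty with variance 1, 52-week look-back, 168 per arm, 400 trials per setting.

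| Observed correlation | Mean SE of log rate ratio, without | With | Ratio |
|---|---|---|---|
| 0 | 0.164 | 0.164 | 1.00 |
| 0.27 | 0.164 | 0.157 | 0.96 |
| 0.38 | 0.163 | 0.149 | 0.92 |
| 0.50 | 0.163 | 0.136 | 0.83 |

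The pattern agrees with Step 1, and at zero correlation nothing is lost. The simulation builds the link between prior and later use in by assumption. It shows what a given correlation would buy, not what the correlation is.

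**The case against.** The strongest reply is that this is a preference about efficiency, not an error. Patients are randomized individually, the covariates are named before unblinding, and the 95% interval already allows for chance imbalance. No statement in the plan is contradicted. The benefit also cannot be established from the documents: at ρ = 0.2 the intervals narrow by only 2%. All of that stands, and it limits the point to an inexpensive improvement.

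The reply is also right on several details:

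- The deprivation index is a socioeconomic measure, so the planned adjustment goes somewhat beyond demographics.
- No look-back period is stated. That earlier encounters can be retrieved is a sound inference from the description of the Research Derivative. For earlier costs the inference is weaker, because the named source is the financial systems.
- The SAP's spline rule would use at least two degrees of freedom for a continuous covariate, and a short prior window with many zeros may not support the knots.
- Protocol section 7.0 limits abstraction to the minimum necessary health information, so pre-enrolment records may need justifying.

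A reader might extend the argument to hospital and ED free days (item g). The documents do not support that. Item g states no VUH limit. Secondary endpoints are said to be collected from randomization, which takes place during the inpatient stay, so free days can include the rest of the index stay. Death is scored as −1. Prior VUH use is not clearly the same measure.

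**Conclusion.** The point holds as an optional gain in precision for items f and j. Its size depends on a correlation the documents do not give: slight at 0.2 to 0.3, worthwhile at 0.5, and nil, without material loss, at zero. It rests on earlier encounters and costs being retrievable and on prior use predicting later use at the same institution.

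Three stronger readings are tempting and not supported:

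- That the planned comparison is biased or invalid. Randomization protects it; the issue is lost precision and the absence of adjustment for a chance imbalance in prior use.
- That power would rise from 80% to some stated higher figure. The 80% belongs to the length-of-stay calculation. Nothing in the documents gives the power of the utilization or cost comparisons.
- That the primary result is affected. The point concerns these two secondary endpoints only.

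**What to change.** Before unblinding, add a sentence to the SAP's Main Analysis section, for items f and j only. Each model gains one covariate measured over a fixed, stated window that ends before the index admission:

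- Item f: log(1 + number of prior VUH ED visits and admissions).
- Item j: log(1 + prior VUMC cost).

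Enter each as a single linear term, expressly exempt from the spline rule. Count a patient with no prior record as zero, which is consistent with outcomes that see only this institution. Exclude the index stay, because it contains the primary outcome. If the zero-inflated Poisson option is kept for item f, say whether the term also enters the inflation part.

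The cost is one more date range in the extraction, possibly a protocol or IRB note under the minimum-necessary wording, and one degree of freedom per model (two for item f if the term enters both parts of a zero-inflated model). If the correlation proves low, little is gained.

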### *Randomization:*

Randomization occurs at the individual patient level. The Bridge Clinic can only accept a limited number of patients, so eligible patients will be randomized in a ratio so that the Bridge Clinic is at capacity. To start, the ratio will be 1:1, and can be updated as often as bi-weekly to maintain the Bridge Clinic capacity. There has been no indication or need to change the ratio during the study.

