### *Sample Size Considerations:*

We estimated about 700 patients per year would be eligible for this study, with a capacity for about 3-4 new patients a week to be seen at the Bridge Clinic. We expected about 2/3 of patients referred to the Bridge Clinic to make their first appointment. The mean length of stay was 15 days with a standard deviation of about 15 days. Assuming a reduced standard deviation of 10 days, with 700 patients a year and a 1:1 randomization ratio, we would have 80% power to detect a 3-day reduction in length of stay. If the standard deviation remains at 15 days, we would have 80% power to detect a 3.5-day reduction in length of stay. Due to COVID-19, enrollment was lower than expected and hospital inpatient experiences differed from historical data. Midway through the recruitment period, the overall, ungrouped distribution of length of stay was re-estimated based on participant experience. Based on the revised assumptions, to detect a 1.5-day

reduction in length of stay and assuming the observed common standard deviation is a good estimate, about 336 patients (168 per group) is needed to have 80% power.

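### The SAP offers zero-inflated Poisson or negative binomial for count endpoints with no selection rule, robust variance or named treatment effect, so valid intervals depend on an unguarded model choice

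*SAP*

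**What the plan says.** The SAP's Main Analysis section covers all counts in one sentence: "For counts, such as number of medication refills, either a zero-inflated Poisson or a negative binomial model will be fit". It applies to at least three secondary endpoints:

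- (c), the self-reported count of medication fills: "prescriptions filled (number filled) at the 16-week follow-up call"
- (e), a second self-reported count: "Number of recurrent opioid uses reported at the 16-week phone call follow-up"
- (f), a count of acute hospital use, covering emergency visits and repeat admissions after discharge, taken from the hospital's own records

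The section does not say how the choice is made, whether dispersion or excess zeros will be checked, what enters the zero part, which variance estimator is used, or which coefficient is the treatment effect. Protocol section 10.0 names models for costs, binary outcomes and quality of life, but none for counts.

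The interval is the main reported result for these endpoints. The SAP's wording on this is: "95% confidence intervals (CIs), which will be emphasized over p-values when reporting the results for secondary and implementation outcomes".

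**The concern.** Zero-inflated Poisson (ZIP) assumes that, apart from the excess zeros, the counts are Poisson, with variance equal to the mean. If some patients have many more events than that allows, its standard error is too small. The negative binomial (NB) allows extra variance. If the true pattern is a block of zeros plus ordinary Poisson counts, however, its model-based standard error is too large. The plan permits either model and has no safeguard against the wrong one.

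There is also a question of what is estimated. Protocol section 1.0 hypothesises lower readmission and recurrent-use rates and higher fill rates with Bridge Clinic referral. For a count endpoint, that is a statement about mean counts. ZIP with arm in both parts yields an odds ratio for being an excess zero and a ratio of counts in the remaining group. Neither is the ratio of mean counts.

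Because secondary results are to be read from their intervals, an interval of the wrong width, or one attached to the wrong quantity, goes straight into the reported finding.

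**Working it through.** **Inputs from the documents.** The simulated size is 168 per arm (SAP, Sample Size Considerations: "about 336 patients (168 per group) is needed to have 80% power") with 1:1 allocation (SAP, Randomization: "There has been no indication or need to change the ratio during the study"). The SAP's 0.05 level is stated for the primary outcome only, without sidedness ("a critical p-value of 0.05 for the effect of treatment group assignment on the primary outcome will be used"); two-sided 5% and 95% intervals are assumed here.

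**Inputs assumed.** The documents give no mean, variance or zero fraction for any count, so these are varied over a range.

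**The plan's own figure.** There is none for counts. The 168 belongs to length of stay and serves only as the simulation size. From the protocol's Interim Analysis inputs, 2 × (1.960 + 0.842)² × (ln 2.7)² / (ln(5.5/4.0))² gives 153 per group rather than 168. That difference has no bearing on this point.

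**Formulas.** NB with mean μ and dispersion a: variance = μ + aμ² (size k = 1/a). ZIP with excess-zero probability π and count-part mean λ: overall mean = (1 − π)λ. The ZIP ratio of means is therefore [(1 − π₁)/(1 − π₀)] × (λ₁/λ₀), which mixes both parts. If r is the average model standard error divided by the true standard deviation of the estimate, the coverage of a nominal 95% interval is roughly 2Φ(1.96r) − 1.

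**Step 1: mismatched model.** Null trials, 168 per arm, 1,000 replicates per row (Monte Carlo error about 0.7 points), no covariates.

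| Data | Fitted | Setting | r | Simulated coverage | 2Φ(1.96r) − 1 |
|---|---|---|---|---|---|
| NB | ZIP count part | μ = 1, a = 0.5 | 0.88 | about 92% | 92% |
| NB | ZIP count part | μ = 3, a = 1 | 0.55 | 72% | 72% |
| NB | ZIP count part | μ = 3, a = 2 | 0.43 | 60% | 60% |
| NB | ZIP count part | μ = 8, a = 3 | 0.22 | 32% | 33% |
| ZIP | NB, model-based | λ = 2, π = 0.3 | 1.03 | 95.4% | 95.7% |
| ZIP | NB, model-based | λ = 4, π = 0.4 | 1.25 | 98.9% | 98.6% |
| ZIP | NB, model-based | λ = 8, π = 0.5 | 1.55 | 99.7% | 99.8% |

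Deriving the overall mean ratio from ZIP softens the undercoverage on NB data but does not remove it: coverage 93% down to 64%. Expressed as false rejection over six NB settings (mean 1 to 10, size 0.4 to 2), the ZIP count-part test rejects 16% to 68% of the time against a nominal 5%. NB on the same data rejects 4% to 6%.

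**Step 2: matched model.** NB on NB data covers 94.0% to 95.9%; ZIP on ZIP data covers 94.1% to 96.1%.

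**Step 3: both features.** With NB counts plus excess zeros (mean 4, a = 0.3 to 1, 30% to 50% excess zeros), ZIP count-part coverage is 68% to 84%, the ZIP-derived mean ratio 85% to 91%, and NB 97% to 98%. Choosing ZIP or NB by AIC when both features are present gives 6% to 12% false rejection, or 7% to 17% if either ZIP coefficient may count. The robust mean ratio gives 4% to 6%.

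**Step 4: what ZIP estimates.** Move from λ = 4, π = 0.5 to λ = 3, π = 0.3.

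- Count ratio: 3/4 = 0.75.
- Excess-zero odds ratio: (0.3/0.7)/(0.5/0.5) = 0.43.
- Overall means: 0.5 × 4 = 2.0 and 0.7 × 3 = 2.1, so the mean ratio is 1.05.

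The count coefficient is significant in 94% of replicates and the mean ratio in 7%. A report built on the count coefficient would say events fell by a quarter when the mean rose slightly. Even when ZIP is exactly true, having two coefficients to read gives about 1 − 0.95² = 9.8% chance of at least one false rejection; simulation gave 9% to 11%.

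**Step 5: ratio of means with robust standard error, same data.** Coverage is 93.6% to 95.9% (NB data), 94.1% to 95.5% (ZIP data) and 93.7% to 96.2% (both features). Power also improves over model-based NB on ZIP data: with excess zeros 50% against 35%, 58% against 38% at λ = 4, and 68% against 27% at λ = 8.

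**The case against.** The strongest reply is that ZIP and NB are standard models for two familiar data shapes, and a competent analyst will pick the one that fits. The SAP commits to describing every outcome before modelling, so the shape will be known. Selection by AIC does work when one model is true: over the six NB and three ZIP settings, the chosen model rejected 3.8% to 6.8% of null trials. This stands, and it limits the point. A reader might infer that both options give wrong error bars, or that no valid interval is available under the plan. The documents do not support that: each model is nominal when it fits, and NB already handles plain overdispersion. What remains is that the SAP states no selection rule, that its descriptive step shows outcomes by arm before the choice need be made, and that AIC between these two models fails when both features are present.

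A reader might also infer that ZIP intervals would be badly narrow in this trial. The documents do not say that visits or uses cluster in a few patients, and at low means with mild dispersion the undercoverage is small (about 92%). Likewise, ZIP does not inherently lack a single effect: a mean ratio can be derived, or arm confined to one part, if the plan says so. The gap is that it does not.

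NB's excess width is conservative. It costs power rather than creating false positives.

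Finally, robust errors are not uniformly safer. Endpoints (c) and (e) come from a telephone call, and analysed numbers may fall below 168 per arm. With 50 per arm and extreme dispersion (assumed), robust Poisson rejected 9.1% (mean 10, size 0.15) and 8.7% (mean 3, size 0.2), against 6.4% and 6.8% for NB. That also stands, and is a reason to keep model-based NB as a sensitivity analysis.

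**Conclusion.** The point holds as a gap in the specification that can produce materially wrong intervals. It does not show that either model is invalid in itself. Depending on dispersion, nominal 95% ZIP count-part intervals cover from about 92% down to 32% on overdispersed counts. NB standard errors run from 3% to 55% too large on purely zero-inflated counts. Selection by fit leaves 6% to 12% false rejection when both features occur. The missing treatment effect under ZIP is a separate gap that needs no assumption about dispersion.

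The sizes rest on assumed means, dispersions and zero fractions, on 168 per arm with full follow-up, and on unadjusted two-arm comparisons. At 100 per arm and mean 1 the pattern was the same: ZIP count-part coverage 92%, 88% and 80% at a = 0.5, 1 and 2. Only secondary endpoints are involved. The 0.05 decision rule applies to length of stay, and the primary conclusion is unaffected. The plan should be changed, but nothing about the trial's main result turns on it.

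**What to change.** Replace the sentence on counts with a rule along these lines. For endpoints (c), (e) and (f), the treatment effect is the ratio of mean counts, Bridge Clinic to usual care, with its 95% confidence interval. It is estimated from one prespecified log-link model (Poisson quasi-likelihood or negative binomial, named in advance) with robust (sandwich) standard errors and the same covariates as the primary model. ZIP is dropped as a main option. Model-based NB or ZIP may be reported as sensitivity analyses; if ZIP is used, its implied mean ratio should be given alongside the two coefficients.

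The cost is a change of SAP wording, with no new data. The statistical price is a slight loss of efficiency against a correctly specified parametric model, and mild inflation of false rejection if follow-up is low and dispersion extreme. The SAP's Introduction places it before final data collection and unblinding, so the change should be made while that still holds.
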